**Amendment [a]****Overall Rationale for the Amendment:**

The protocol is being amended to remove language specific to case report form entry.

Section # and Name	Description of Change	Brief Rationale
Section 8 Study Assessments and Procedures	Removed bullet 5.	To remove language regarding sample collection actual time case report form (CRF) entry for consistency with the study electronic case report form (eCRF) build.

## 1. Protocol Summary

### 1.1. Synopsis

**Protocol Title:**

A Phase 1, Open-Label, Drug Interaction Study to Investigate the Effect of Single Dose Selpercatinib on the Pharmacokinetics of Rosuvastatin in Healthy Participants

**Brief Title:**

A drug interaction study to investigate the effect of selpercatinib on the pharmacokinetics of rosuvastatin.

**Regulatory Agency Identifier Number:**

IND: 133193

**Rationale:**

Rosuvastatin is a commonly used index substrate for breast cancer resistance protein (BCRP) (FDA, 2021). Selpercatinib may potentially inhibit BCRP in the intestine according to in vitro evaluation. Therefore, this study aims to investigate a potential drug-drug interaction (DDI) by evaluating the pharmacokinetics (PK), safety, and tolerability of rosuvastatin in the presence of selpercatinib.

**Objectives and Endpoints:**

Objectives	Endpoints
Primary	

To evaluate the effect of a single dose of selpercatinib on BCRP activity in healthy participants

	

<math>C_{max}</math> and <math>AUC_{(0-\infty)}</math> of rosuvastatin

Secondary	

To describe the safety and tolerability of rosuvastatin in combination with selpercatinib in healthy participants

	

Incidence of TEAEs and SAEs

Abbreviations:  $AUC_{(0-\infty)}$  = area under the concentration versus time curve from time zero to infinity; BCRP = breast cancer resistance protein;  $C_{max}$  = maximum observed drug concentration; SAE = serious adverse event; TEAE = treatment-emergent adverse event.

**Overall Design:**

Study J2G-MC-JZPB is a Phase 1, open-label, fixed-sequence, drug interaction study to investigate the effect of a single dose of selpercatinib on the PK of rosuvastatin in healthy participants.

**Brief Summary:**

The purpose of this study is to investigate a potential DDI by measuring PK of rosuvastatin with selpercatinib in healthy participants.

Study details include:

- The study duration will be approximately 8 weeks.
- The study intervention will be administered on Days 1 and 5.
- The visit frequency will be 9 continuous days in the clinical research unit (CRU).

**Study Population:**

Healthy participants will be enrolled in this study.

**Number of Participants:**

Approximately 28 participants will be enrolled to ensure that at least 20 evaluable participants complete the study.

**Intervention Groups and Duration:**

All participants will be screened for inclusion within 42 days prior to enrollment. Eligible participants will be admitted to the CRU on Day -1 and remain resident in the CRU until discharge on Day 8. A follow-up visit will be performed 7 to 10 days (Days 12 to 15) after the final dose of study intervention.

Participants will receive the following study intervention while resident in the CRU:

- Day 1: 20 mg rosuvastatin alone
- Day 5: 20 mg rosuvastatin coadministered simultaneously with 160 mg selpercatinib

**Ethical Considerations of Benefit/Risk:**

[figure not shown]
The following are the risks and discomforts associated with selpercatinib: dry mouth, diarrhea, hypertension, fatigue, constipation, alanine aminotransferase (ALT)/aspartate aminotransferase (AST) elevation, headache, nausea, edema peripheral, abdominal pain, rash, electrocardiogram QT prolonged, cough, vomiting, dyspnea, and increased blood creatinine.

Adverse events of special interest include hypersensitivity, liver injury, QT prolongation, and hypertension. Therefore, these reactions will be monitored during the course of the study.

The following are the risks and discomforts associated with rosuvastatin: headache, myalgia, abdominal pain, asthenia, nausea, ALT/AST elevation, myopathy, and rhabdomyolysis.

**Data Monitoring Committee: No**

## 1.2. Schema

Abbreviation: CRU = clinical research unit

### 1.3. Schedule of Activities (SoA)

Study Procedure	Screening	Treatment										FU/ED	Comments
		-1	1	2	3	4	5	6	7	8	12 to 15		
Study Day	-42 to -2												
Informed consent	X												
Medical history and demographics	X	X											
Admission to CRU		X											
Discharge from CRU											X		
Outpatient visit	X											X	
Participant eligibility	X	X											
Height and weight	X	X										X	Height: screening only.
Physical examination		X										X	Day -1: Full examination. Day 8: Symptom-driven examination.
Pregnancy test	X	X										X	Serum pregnancy test: screening. Urine pregnancy test: all other time points.
FSH	X												See Section 10.4.1.
Serology	X												
Clinical laboratory tests	X	X			X		P		X		X		
12-lead ECG (hr)	X		P				P, 2, 4	24	48	72	X		
Vital signs and body temperature (supine) (hr)	X	X	P	24	X	X	P, 1, 2	24	X	X	X		Temperature: screening and Day -1.
Ethanol test	X	X											
Urine drug screen	X	X											

Study Procedure	Screening	Treatment										FU/ED	Comments
		-42 to -2	-1	1	2	3	4	5	6	7	8		
Study Day	-42 to -2												
Genetic blood sample for screening	X												
Pharmacogenetic blood sample for storage			P										
Rosuvastatin administration				X					X				
Selpercatinib administration									X				
Rosuvastatin PK samples (hr)													
Selpercatinib PK samples (hr)													
Plasma coproporphyrin I samples (hr)													
Adverse events			X	X	X	X	X	X	X	X	X		
Concomitant medications	X	X	X	X	X	X	X	X	X	X	X		

Abbreviations: CRU = clinical research unit; ECG = electrocardiogram; ED = early discontinuation; FSH = follicle stimulating hormone; FU = follow-up;

hr = hour; P = predose; PK = pharmacokinetics.

## 2. Introduction

### 2.1. Study Rationale

The breast cancer resistance protein (BCRP) is a membrane-bound transporter located in the gastrointestinal tract, liver, kidney, brain endothelium, mammary tissue, testis, and placenta, responsible for exporting a wide range of substrates across biological membranes. Certain substrates of BCRP have been shown to have clinically significant drug interactions when administered with inhibitors of BCRP (International Transporter Consortium et al. 2010).

Rosuvastatin is a commonly used index substrate for BCRP (FDA, 2021). Selpercatinib may potentially inhibit BCRP in the intestine according to in vitro evaluation. Therefore, this study aims to investigate a potential drug-drug interaction (DDI) by evaluating the pharmacokinetics (PK), safety, and tolerability of rosuvastatin in the presence of selpercatinib.

### 2.2. Background

Selpercatinib (LY3527723, Retevmo®) is a orally available, highly selective, adenosine triphosphate (ATP)-competitive small molecule inhibitor of the *REarranged during Transfection (RET)* gene receptor tyrosine kinase (RTK) approved by the FDA for the treatment of

- adult patients with locally advanced or metastatic non-small cell lung cancer (NSCLC) with a *RET* gene fusion, as detected by an FDA-approved test
- adult and pediatric patients 12 years of age and older with advanced or metastatic medullary thyroid cancer (MTC) with a *RET* mutation, as detected by an FDA-approved test, who require systemic therapy
- adult and pediatric patients 12 years of age and older with advanced or metastatic thyroid cancer with a *RET* gene fusion, as detected by an FDA-approved test, who require systemic therapy and who are radioactive iodine-refractory (if radioactive iodine is appropriate)
- adult patients with locally advanced or metastatic solid tumors with a *RET* gene fusion that have progressed on or following prior systemic treatment or who have no satisfactory alternative treatment options

Across clinical studies, single oral doses of selpercatinib were administered over a range of 20 to 720 mg. In studies (LOXO-RET-18017 and LOXO-RET-18026), multiple oral doses of 160 mg/day selpercatinib were administered orally twice daily for 10 days in healthy participants.

In healthy participants, the median (range) time to maximum drug concentration ( $t_{max}$ ) of selpercatinib is 2 (1.5 to 6.0) hours and selpercatinib is eliminated with a mean (range) terminal elimination half-life ( $t_{1/2}$ ) of 13.6 (9.82 to 19.6) hours.

More detailed information about the PK and absorption, distribution, metabolism, and excretion properties of selpercatinib may be found in the Investigator's Brochure (IB).

## 2.3. Benefit/Risk Assessment

There is no anticipated therapeutic benefit for the participants in this study. However, participants may benefit from the screening procedures (through detection of unknown health issues) even if they receive no therapeutic benefit from the study.

The single dose of selpercatinib to be given in this study is 160 mg (2 × 80-mg capsules), as it is the highest approved dose by the FDA. The safety profile of selpercatinib shows that selpercatinib is very well tolerated in healthy participants and is clinically manageable, with low rates of study drug discontinuation due to adverse events (AEs). As outlined in the IB, the most common toxicities associated with selpercatinib are monitorable and reversible, and include dry mouth, diarrhea, hypertension, fatigue, constipation, aspartate aminotransferase (AST)/ alanine aminotransferase (ALT) elevation, headache, nausea, edema peripheral, abdominal pain, rash, electrocardiogram (ECG) QT prolonged, cough, vomiting, dyspnea, and increased blood creatinine. Adverse events of special interest include hypersensitivity, liver injury, QT prolongation, and hypertension. In a recently completed DDI study with dabigatran in healthy participants (Study J2G-MC-JZJV), only 1 treatment-emergent adverse event (TEAE) considered to be related to selpercatinib was reported (dyspepsia). In a single 160-mg dose, crossover bioequivalent study in 224 healthy participants (Study J2G-MC-JZJZ), the most frequently reported TEAEs following dosing was headache (20 events in 16 participants) followed by COVID-19 (13 events in 13 participants). Four AEs of ALT increased and 2 AEs of AST increased were reported, all were mild in severity and resolved by the end of the study.

More detailed information about the known and expected benefits and risks and reasonably expected AEs of selpercatinib may be found in the IB.

Rosuvastatin is a commonly used drug in DDI studies and the dosing regimen in the current study (20 mg) is consistent with the prescribing recommendations. The most frequent ( $\geq 2\%$ ) adverse reactions following rosuvastatin dosing are headache, myalgia, abdominal pain, asthenia, and nausea. Cases of myopathy and rhabdomyolysis have been reported with rosuvastatin. These risks can occur at any dose level, but are increased at the highest dose of 40 mg. The incidence of rhabdomyolysis is 0.3 to 13.5 cases per 1,000,000 (Mendes et al. 2014). During the current study, participants should promptly report any unexplained muscle pain, tenderness, or weakness. Elevations in liver enzymes (ALT and AST) have been reported following rosuvastatin dosing. In most cases, the elevations were transient and resolved or improved on continued dosing or after brief interruption of dosing. In the current study, blood samples to determine liver enzymes (as part of clinical laboratory tests) will be collected prior to each dosing occasion of rosuvastatin.

More detailed information about the known and expected benefits and risk and reasonably expected AEs of rosuvastatin may be found in the prescribing information (Crestor® Prescribing Information, 2020).

### 3. Objectives and Endpoints

Objectives	Endpoints
Primary	

 
To evaluate the effect of a single dose of selpercatinib on BCRP activity in healthy participants
 
	
 
<math>C_{max}</math> and <math>AUC_{(0-\infty)}</math> of rosuvastatin
 

Secondary	

 
To describe the safety and tolerability of rosuvastatin in combination with selpercatinib in healthy participants
 
	
 
Incidence of TEAEs and SAEs
 

Exploratory	

 
To assess the exploratory measurement of plasma coproporphyrin I as biomarker of transporter OATP1B1 and OATP1B3 inhibition in healthy participants to further inform degree of transporter inhibition risk
 
	
 
Plasma concentrations of biomarker coproporphyrin I: <math>C_{max}</math> and <math>AUC_{(0-24)}</math>
 

Abbreviations:  $AUC_{(0-\infty)}$  = area under the concentration versus time curve from time zero to infinity;  $AUC_{(0-24)}$  = area under the concentration versus time curve from time zero to 24 hours; BCRP = breast cancer resistance protein;  $C_{max}$  = maximum observed drug concentration; OATP = organic anion transporting polypeptide; SAE = serious adverse event; TEAE = treatment-emergent adverse event.

## 4. Study Design

### 4.1. Overall Design

Study J2G-MC-JZPB is a Phase 1, open-label, fixed-sequence, drug interaction study to investigate the effect of a single dose of selpercatinib on the PK of rosuvastatin in healthy participants.

The schema in Section 1.2 illustrates the study design.

Approximately 28 participants will be enrolled to ensure that at least 20 evaluable participants complete the study.

#### Screening

All participants will be screened for study inclusion within 42 days prior to enrollment (Day 1). Screening should not occur less than 14 days prior to enrollment (Day 1) in order to allow sufficient time to receive genotyping results.

#### Treatment and Assessment Period

Participants will check in to the clinical research unit (CRU) on Day -1 and remain resident until discharge on Day 8.

While resident at the CRU, all participants will receive study intervention as follows:

- Day 1: 20 mg rosuvastatin alone
- Day 5: 20 mg rosuvastatin coadministered simultaneously with 160 mg selpercatinib

Pharmacokinetic blood sampling and safety assessments, including vital signs measurements, physical examinations, clinical laboratory tests, ECGs, and AE recording, will be performed according to the Schedule of Activities (SoA; Section 1.3)

Participants will be discharged from the CRU on Day 8 following completion of study procedures, provided they are deemed medically fit by the investigator or designee.

#### Follow-up

Participants will attend an outpatient follow-up visit 7 to 10 days (Days 12 to 15) after the final dose of rosuvastatin coadministered with a single dose of selpercatinib. If participants are not able to attend the CRU for this visit, the CRU should contact the participant via phone call to conduct AE and concomitant medication review.

### 4.2. Scientific Rationale for Study Design

To allow each participant to act as their own control for safety and PK comparisons, a fixed sequence design has been selected. This study will be open label as the study primary endpoint PK measures are objective rather than subjective.

Based on the  $t_{1/2}$  of rosuvastatin from label (19 hours; Crestor Prescribing Information, 2020) or observed from Study J2N-MC-JZNW (geometric mean of 8.21 hours with range of 3.02 to 39.8 hours), a period of 4 days between rosuvastatin doses is considered sufficient time for the study intervention to washout.

The PK of rosuvastatin will be evaluated after a single dose on Day 1 and again on Day 5, coadministered simultaneously with selpercatinib, to assess the effect of selpercatinib on intestinal BCRP.

Conducting the study in healthy participants mitigates the potential confounding effects of any disease state, other medical conditions, and concomitant medications in patients.

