Formatting of tables, figures and abbreviations will follow the Eli Lilly Global PK/PD/TS Tool: NON-COMPARTMENTAL PHARMACOKINETIC STYLE GUIDE. The version of the tool effective at the time of PK analysis will be followed.

General PK Parameter Rules

- Actual sampling times will be used in the final analyses of individual PK parameters, except for non-bolus pre-dose sampling times which will be set to zero. For non-bolus, multiple dose profiles, the pre-dose time will be set to zero unless a time deviation falls outside of the protocol blood collection time window which is considered to impact PK parameter derivation.
- C_{max} and t_{max} will be reported from observed values. If C_{max} occurs at more than one time point, t_{max} will be assigned to the first occurrence of C_{max}.
- AUC parameters will be calculated using a combination of the linear and logarithmic trapezoidal methods (linear-log trapezoidal rule). The linear trapezoidal method will be applied up to t_{max} and then the logarithmic trapezoidal method will be used after t_{max}. The minimum requirement for the calculation of AUC will be the inclusion of at least three consecutive plasma concentrations above the lower limit of quantification (LLOQ), with at least one of these concentrations following C_{max}. AUC(0-∞) values where the percentage of the total area extrapolated is more than 20% will be flagged. Any AUC(0-∞) value excluded from summary statistics will be noted in the footnote of the summary table.
- Half-life (t_{1/2}) will be calculated, when appropriate, based on the apparent terminal log-linear portion of the concentration-time curve. The start of the terminal elimination phase for each participant will be defined by visual inspection and generally will be the first point at which there is no systematic deviation from the log-linear decline in plasma concentrations. Half-life will only be calculated when a reliable estimate for this parameter can be obtained comprising of at least 3 data points. If t_{1/2} is estimated over a

time window of less than 2 half-lives, the values will be flagged in the data listings. Any $t_{1/2}$ value excluded from summary statistics will be documented in the footnote of the summary table.

- A uniform weighting scheme will be used in the regression analysis of the terminal log-linear portion of the concentration-time curve.

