- A concentration average will be plotted for a given sampling time only if 2/3 of the individual data at the time point have quantifiable measurements that are within the sampling time window specified in the protocol or $\pm 10\%$. An average concentration estimated with less than 2/3 but more than 3 data points may be displayed on the mean concentration plot if determined to be appropriate and will be documented within the final study report.

Treatment of Outliers during Pharmacokinetic Analysis

Application of this procedure to all PK analyses is not a requirement. Rather, this procedure provides justification for exclusion of data when scientifically appropriate. This procedure describes the methodology for identifying an individual value as an outlier for potential exclusion, but does not require that the value be excluded from analysis. The following methodology will not be used to exclude complete profiles from analysis.

Data within an Individual Profile

A value within an individual profile may be excluded from analysis if any of the following criteria are met:

- For PK profiles during multiple dosing, the concentration of the pre-dose sample exceeds all measured concentrations for that individual in the subsequent postdose samples.
- For PK profiles during single dosing of non-endogenous compounds, the concentration in a pre-dose sample is quantifiable.
- For any questionable datum that does not satisfy the above criteria, the profile will be evaluated and results reported with and without the suspected datum.

Data between Individual Profiles

1. If $n < 6$, then the dataset is too small to conduct a reliable range test. Data will be analyzed with and without the atypical value, and both sets of results will be reported.
2. If $n \geq 6$, then an objective outlier test will be used to compare the atypical value to other values included in that calculation:
 - a. Transform all values in the calculation to the logarithmic domain.

- b. Find the most extreme value from the arithmetic mean of the log transformed values and exclude that value from the dataset.
- c. Calculate the lower and upper bounds of the range defined by the arithmetic mean $\pm 3*SD$ of the remaining log-transformed values.
- d. If the extreme value is within the range of arithmetic mean $\pm 3*SD$, then it is not an outlier and will be retained in the dataset.

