- e. If the extreme value is outside the range of arithmetic mean $\pm 3*SD$, then it is an outlier and will be excluded from analysis.

If the remaining dataset contains another atypical datum suspected to be an outlier and $n \geq 6$ following the exclusion, then repeat step 2 above. This evaluation may be repeated as many times as necessary, excluding only one suspected outlier in each iteration, until all data remaining in the dataset fall within the range of arithmetic mean $\pm 3*SD$ of the log-transformed values.

Reporting of Excluded Values

Individual values excluded as outliers will be documented in the final report. Approval of the final report will connote approval of the exclusion.

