10.3.2 Pharmacokinetic Statistical Methodology

Rosuvastatin

Log-transformed C_{max} and $AUC(0-\infty)$ of rosuvastatin will be evaluated in a linear mixed-effects model with fixed effects for treatment and a random effect for participant. The treatment differences will be back-transformed to present the ratios of geometric least squares means and the corresponding 90% CIs. The test treatment is rosuvastatin in the presence of selpercatinib, and reference treatment is rosuvastatin alone.

The parameter t_{max} of rosuvastatin will be analyzed non-parametrically. Estimates of the median for each treatment, median of the within-participant differences, approximate 90% CI for the difference, and p-value from the Wilcoxon signed-rank test will be calculated.

Example of the SAS code that will be used are as follows:

Mixed Model Analysis

CCI

Signed rank test (tmax)

CCI

Coproporphyrin 1

The effect of a single dose of selpercatinib (Day 5) on plasma coproporphyrin I, a biomarker of OATP inhibition in healthy participants, will be explored.

Log-transformed C_{max} and $AUC(0-24)$ of coproporphyrin I will be evaluated in a linear mixed-effects model with fixed effects for treatment and a random effect for participant. The treatment differences will be back-transformed to present the ratios of geometric least squares means and the corresponding 90% CIs. The test treatment is coproporphyrin I in the presence of rosuvastatin and selpercatinib (Day 5), and reference treatment is coproporphyrin I in the presence of rosuvastatin (Day 1).

The SAS code will be similar to that above.

Selpercatinib

The PK parameters of selpercatinib will be summarized and listed. No inferential statistical analyses are planned.

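### Does a 4-day washout that is short at the quoted 39.8 h half-life call for a carryover correction to the Day 5 rosuvastatin ratio?

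*Protocol*

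**What the plan says.** Protocol 4.2 justifies the interval by two half-life sources: the label value of 19 h, and an earlier study with a "geometric mean of 8.21 hours with range of 3.02 to 39.8 hours". From these it concludes that "a period of 4 days between rosuvastatin doses is considered sufficient time for the study intervention to washout". It does not comment on the upper end of the range.

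Under SAP 10.3.2, log Cmax and log AUC(0-∞) are "evaluated in a linear mixed-effects model with fixed effects for treatment and a random effect for participant". There is no period or carryover term.

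The outlier rules in SAP 10.3.1 list values within a profile that may be left out. One criterion reads: "For PK profiles during single dosing of non-endogenous compounds, the concentration in a pre-dose sample is quantifiable". The same section says the procedure is optional and need not lead to exclusion, and adds: "The following methodology will not be used to exclude complete profiles from analysis". It also states: "Individual values excluded as outliers will be documented in the final report".

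SAP 10.3.1 also derives the percentage of AUC(0-∞) extrapolated for rosuvastatin and flags AUC(0-∞) when that exceeds 20%. When a half-life is estimated over a "time window of less than 2 half-lives, the values will be flagged in the data listings". SAP 10.1 lists all databased data.

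**The concern.** The protocol calls the interval sufficient while quoting a half-life at which it is not. A participant at 39.8 h would begin Day 5 with nearly a fifth of the Day 1 drug still to be eliminated.

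Every participant takes rosuvastatin alone first, so the residue can enter only the test profile. With treatment as the only fixed effect, the model attributes it to inhibition by selpercatinib. The bias has one direction, towards a larger interaction, in both primary parameters.

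The SAP's one rule that touches the matter treats a quantifiable predose value as a candidate for removal. It does not use that value to estimate the carryover. At stake is whether part of the reported ratio could be left-over drug, with no prespecified analysis to show how much.

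**Working it through.** **Inputs.** Dosing interval 96 h (Day 1 to Day 5). Half-lives 8.21 h, 19 h and 39.8 h (Protocol 4.2). 20 evaluable participants and intra-participant CV 33% (Protocol 9.5, SAP 8). Assumed, because the documents do not give them: the spread of half-lives, the share *f* of AUC in the terminal phase, the true ratio *R*, and the sampling times, which are not visible in the public copy.

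**1. Residual drug at the Day 5 dose.** Residual = 2^(−96/t½).

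| t½ (h) | 96/t½ | Residual |
|---|---|---|
| 8.21 | 11.7 | 0.03% |
| 19 | 5.05 | 3.0% |
| 39.8 | 2.41 | 18.8% |

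Five half-lives fit into 96 h up to 96/5 = 19.2 h. So the protocol's statement reproduces at both central values and fails only at the extreme. Five half-lives is the washout yardstick in exclusion criterion 25 (Protocol 5.2), which was set for prior investigational products.

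**2. Planned precision.** Within-participant log SD = √ln(1 + 0.33²) = 0.3215. Expected 90% CI half-width = t(0.95, 19) × 0.3215 × √(2/20) = 1.729 × 0.3215 × 0.3162 = 0.176 on the log scale, a factor of 1.19.

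**3. Effect on the geometric mean ratio.** Bias = exp{mean of ln(1 + f × residual / R)} − 1.

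- One participant at 39.8 h among 20, f = 1, R = 1: exp(ln(1.188)/20) − 1 = 0.86%. Two such participants: 1.7%. One, with R = 2: 0.45%.
- Log-normal half-lives centred on 8.21 h, log SD 0.40 to 0.79: 0.3% to 1.7% with f = 1, R = 1, and 0.07% to 0.5% with f = 0.5, R = 2. The upper log SD is ln(39.8/3.02) = 2.58 divided by the expected normal range for n = 12. The earlier study's size is not given, and 0.40 is an assumed lower value.
- Every participant at 19 h: 3.0%. With a log SD of 0.4 to 0.6 around 19 h: 4.8% to about 6.5%. At 0.6, however, 10.9% of simulated participants exceed 39.8 h, the longest half-life quoted. Restricting draws to 3.02–39.8 h brings the 6.5% down to 4.2%.

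On the log scale 0.86% is 0.0086, about one twentieth of 0.176. The 3.0% case is 0.0297, about one sixth.

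**4. What the planned outputs already show.** With linear kinetics and unchanged disposition, residual drug adds to Day 5 AUC(0-∞) exactly the Day 1 AUC beyond 96 h. The last Day 1 sample cannot fall after the Day 5 dose. The Day 1 extrapolated percentage, taken from the last measurable concentration, is therefore an estimated ceiling on that addition. With a mono-exponential decline at 39.8 h, the 20% flag is raised for any last time up to 39.8 × log₂5 = 92.4 h. In an illustrative one-compartment model (absorption rate 0.4/h, sampling to 72 h, both assumed), the extrapolated share is 29.8% at 39.8 h and 8.0% at 19 h. The true carryover shares there are 19.6% and 3.3%. If selpercatinib also slowed elimination, the residue would scale up with the ratio, so for R above 1 the relative bias lies between share/R and the share itself.

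**5. What a change would gain.** In that model at 39.8 h with R = 1, the Day 5/Day 1 AUC ratio is 1.197 with the predose value kept and 1.196 with it dropped. Exempting it from exclusion thus removes no bias. Subtracting a decaying residue removes the bias only if the terminal rate is known. The subtracted area is the predose concentration divided by that rate. A rate 20% too low over-subtracts by a quarter (18.8 × 0.25 = 4.7 points), and one 20% too high leaves a sixth uncorrected (18.8/6 = 3.1 points). At 19 h the same errors are 0.75 and 0.5 points. Two half-lives at 39.8 h take 79.6 of the 96 h, so the slowest participants are those whose rate is least well estimated.

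**The case for a change.** The strongest case for a change is that the bias has a known direction, the design cannot separate it from inhibition, and a prespecified sensitivity analysis is cheap and more credible than one chosen after the ratio is seen. The label half-life of 19 h is as much the protocol's own figure as 8.21 h, and around it the bias could reach several per cent. The extrapolated percentage concerns AUC only. Cmax is also primary, and in the one-compartment model it is inflated as much as AUC (1.197 at 39.8 h).

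Part of this stands. The SAP contains no residual-corrected ratio, Section 4.2 passes over its own upper value, and no planned summary bounds the carryover in Cmax. But the concentrations that would show it are listed, and the effect on the geometric mean is diluted across participants just as for AUC. The figures of 4.8% to 6.5% need a spread that the documents do not supply, and part of them comes from half-lives beyond any quoted.

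No fixed-effect specification in a two-period, fixed-sequence design would separate carryover from treatment, so the model is not at fault. The outlier rule is permissive, and exclusions must be documented. SAP 3 allows supplementary analyses if the data call for them. An upward bias cannot hide an interaction, although it could overstate one.

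**Conclusion.** No change is needed. The arithmetic behind the concern is right: the interval is adequate up to a half-life of about 19 h and short at 39.8 h, where about 19% remains. That figure describes one extreme participant in another study, and this trial excludes some transporter genotypes, one of them explicitly to limit variability in rosuvastatin exposure. The expected effect on the primary ratio is below about 2% with half-lives centred on 8.21 h and about 3% if every participant had 19 h, against a CI half-width of about 19%.

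These sizes rest on first-order decline, an assumed spread of half-lives and true ratios of 1 to 2. They would be smaller if little of the AUC lies in the slow phase, and larger if slow eliminators were common. The Day 1 extrapolated percentages and the listed concentrations would reveal the latter.

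The wording of Section 4.2 is a population-level judgement that leaves its upper value undiscussed. It is not an error that alters the analysis. A correction would leave the primary ratio as it is, would depend on a Day 5 predose sample that cannot be confirmed from the public copy, and would work worst for the participants it is meant for. The planned analysis is a fair trade-off.
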